9.2. HBV-specific Self-stigma PRO Scale

The HBV-specific self-stigma scale is an hepatitis B-specific PRO instrument designed to assess the experience and impact of self-stigma. The current version consists of 37 items. The items cover aspects of self-stigma such as a) devaluation, inferiority, and worthlessness, b) marginalization and alienation, c) secrecy and concealment, d) shame and guilt, and e) withdrawal and social

isolation. Each of the 37 items is graded on a 5-point Likert scale (1=“Never”, 2=“Rarely”, 3=“Sometimes”, 4=“Often”, and 5=“Always”).

The analyses will be performed in a similar manner as described in Section 9.1.

9.3. Patient Global Impression of Change Scale (PGIC)

The PGIC scale is a single-item PRO scale aimed at assessing the participant’s perceptions of change (improvement or worsening) in how they feel overall compared to the beginning of the study. Response options include: “Much better”, “Better”, “A little better”, “No change”, “A little worse”, “Worse”, “Much worse”.

The tabulation of the number and percentage of participants at each response level will be displayed per time point for each intervention arm. The comparison among the intervention arms will be done using Mann–Whitney U test.



ATTACHMENT 1

Selected Major Protocol Deviations for analysis Purposes: The major protocol deviations that may affect the assessment of efficacy will be finalized prior to the primary analysis database lock. Two Per Protocol sets are identified: PP1 to be used for the primary efficacy endpoint (at Week 48) analysis and PP2 for the key secondary efficacy endpoint (at Week 72) analysis. The major deviations that are selected to exclude participants from the PP sets are listed below. The flag of Intercurrent Event is added to each deviation for facilitating the implementation of the estimands for the primary and key secondary efficacy endpoints.

Sequence No.	Protocol Deviation Description (DVTERM)	Protocol Deviation Coded Term (DVDECOD)	Exclude from PP1	Intercurrent Event PP1	Exclude from PP2	Intercurrent Event PP2
1	Inclusion criterion 3 not met: Chronic HBV infection was not documented by serum HBsAg positivity at screening and/or chronicity was not documented by serum HBsAg positivity at least 6 months prior to screening, or by alternative markers of chronicity.	Entered but did not satisfy criteria	Yes	No	Yes	No
2	Inclusion criterion 4 not met: Participant who is currently not treated does not have a. Serum HBV DNA at screening more than or equal to 2,000 IU/mL for HBeAg-negative participants and greater than or equal to 20,000 IU/mL for HBeAg-positive participants and/or b. ALT levels at screening less than 10x ULN AND greater than ULN on 2 sequential measurements at least 3 months apart.	Entered but did not satisfy criteria	Yes	No	Yes	No
3	Inclusion Criterion 5 not met: Participant is not suppressed and/or a. Participant is not on stable NA treatment (ETV, TDF, or TAF) for greater than or equal to 6 months prior to screening and/or not having the same dose for ≥ 3 months prior to screening b. Participant is not having serum HBV DNA < 60 IU/mL on two sequential measurements at least 6 months apart (one of which is at screening) c. Participant is not having ALT values $\leq 2x$ ULN on two sequential.	Entered but did not satisfy criteria	Yes	No	Yes	No
4	Inclusion Criterion 6 not met: Participant has HBsAg ≤ 100 IU/mL at screening.	Entered but did not satisfy criteria	Yes	No	Yes	No
5	Exclusion Criterion 1 met: Participant has evidence of hepatitis A virus infection (hepatitis A antibody IgM), HCV infection (HCV antibody), HDV infection (HDV antibody), or hepatitis E virus infection (hepatitis E antibody IgM), or HIV-1 or HIV 2 infection (confirmed by antibodies) at screening.	Entered but did not satisfy criteria	Yes	No	Yes	No
6	Exclusion Criterion 2 met: Participant has Total bilirubin $> 1.5x$ ULN or Direct bilirubin $> 1.2x$ ULN or Prothrombin time $> 1.3x$ ULN or Serum albumin < 3.2 g/dL within 12 months prior to screening.	Entered but did not satisfy criteria	Yes	No	Yes	No
7	Exclusion Criterion 3 met:	Entered but did not satisfy criteria	Yes	No	Yes	No

Sequence No.	Protocol Deviation Description (DVTERM)	Protocol Deviation Coded Term (DVDECOD)	Exclude from PP1	Intercurrent Event PP1	Exclude from PP2	Intercurrent Event PP2
	Participant has a history or evidence of hepatic decompensation <Specify>.					
8	Exclusion Criterion 4 met: Participant has evidence of <specify liver disease of non-HBV etiology>.	Entered but did not satisfy criteria	Yes	No	Yes	No
9	Subject used disallowed medication at any time prior to screening until end of follow-up: <specify treatment, dose, unit, frequency, reason administered>.	Received a disallowed concomitant treatment	If classified as major protocol deviation, excluded from PP1 set.	Yes	If classified as major protocol deviation, excluded from PP2 set.	Yes
10	Subject used disallowed medication from 6 months prior to screening until end of follow-up: <specify treatment, dose, unit, frequency, reason administered>.	Received a disallowed concomitant treatment	If classified as major protocol deviation, excluded from PP1 set.	Yes	If classified as major protocol deviation, excluded from PP2 set.	Yes
11	Subject used disallowed medication from 6 months prior to screening until end of follow-up: <specify treatment, dose, unit, frequency, reason administered>.	Received a disallowed concomitant treatment	If classified as major protocol deviation, excluded from PP1 set.	Yes	If classified as major protocol deviation, excluded from PP2 set.	Yes
12	Subject used disallowed medication from 1 month prior to screening until end of follow-up: <specify treatment, dose, unit, frequency, reason administered>.	Received a disallowed concomitant treatment	If classified as major protocol deviation, excluded from PP1 set.	Yes	If classified as major protocol deviation, excluded from PP2 set.	Yes
13	Subject used disallowed medication from screening until end of follow-up: <specify treatment, dose, unit, frequency, reason administered>.	Received a disallowed concomitant treatment	If classified as major protocol deviation, excluded from PP1 set.	Yes	If classified as major protocol deviation, excluded from PP2 set.	Yes
14	Subject used disallowed medication from 1 week prior to baseline until 12 weeks after EOS intervention: <specify treatment, dose, unit, frequency, reason administered>.	Received a disallowed concomitant treatment	If classified as major protocol deviation, excluded from PP1 set.	Yes	If classified as major protocol deviation, excluded from PP2 set.	Yes
15	Received wrong treatment of study drug JNJ-6379: was randomized to receive JNJ-6379 but received placebo or vice versa	Received wrong treatment or incorrect dose	If classified as major protocol deviation, excluded from PP1 set.	Yes	If classified as major protocol deviation, excluded from PP2 set.	Yes
16	Received wrong treatment of study drug JNJ-3989: incorrect dose or placebo when randomized to active (and vice versa)	Received wrong treatment or incorrect dose	If classified as major protocol deviation, excluded from PP1 set.	Yes	If classified as major protocol deviation, excluded from PP2 set.	Yes
17	Subject did not receive dose of study drug JNJ-3989 within window: Subject missed two consecutive injections or missed more than 2 injections.	Received wrong treatment or incorrect dose	If classified as major protocol deviation, excluded from PP1 set.	Yes	If classified as major protocol deviation, excluded from PP2 set.	Yes
18	Subject missed more than 5 JNJ-6379/ Placebo doses within a four week period	Received wrong treatment or incorrect dose	If classified as major protocol deviation, excluded from PP1 set.	Yes	If classified as major protocol deviation, excluded from PP2 set.	Yes
19	Subject missed NA treatment for more than 5 doses within a four week period.	Received wrong treatment or incorrect dose	If classified as major protocol deviation, excluded from PP1 set.	Yes	If classified as major protocol deviation, excluded from PP2 set.	Yes
20	Subject received expired study medication <JNJ-3989, JNJ-6379, NA or placebo>.	Received wrong treatment or incorrect dose	If classified as major protocol deviation, excluded from PP1 set.	Yes	If classified as major protocol deviation, excluded from PP2 set.	Yes

Sequence No.	Protocol Deviation Description (DVTERM)	Protocol Deviation Coded Term (DVDECOD)	Exclude from PP1	Intercurrent Event PP1	Exclude from PP2	Intercurrent Event PP2
21	Subject has event of signs of decreasing liver function based on laboratory or clinical findings, but did not start NA treatment.	Received wrong treatment or incorrect dose	If classified as major protocol deviation, excluded from PP1 set.	Yes	If classified as major protocol deviation, excluded from PP2 set.	Yes
22	Subject has confirmed HBeAg seroreversion, but did not start NA treatment.	Received wrong treatment or incorrect dose	If classified as major protocol deviation, excluded from PP1 set.	Yes	If classified as major protocol deviation, excluded from PP2 set.	Yes
23	Subject has a confirmed post-treatment increase in HBV DNA >2,000 IU/mL and ALT >5 x ULN over a period of at least 4 weeks, but did not start NA treatment	Received wrong treatment or incorrect dose	If classified as major protocol deviation, excluded from PP1 set.	Yes	If classified as major protocol deviation, excluded from PP2 set.	Yes
24	Subject has a confirmed post-treatment increase in HBV DNA >20,000 IU/mL over a period of at least 4 weeks, but did not start NA treatment	Received wrong treatment or incorrect dose	If classified as major protocol deviation, excluded from PP1 set.	Yes	If classified as major protocol deviation, excluded from PP2 set.	Yes
25	Subject has confirmed signs of hepatic decompensation <specify> but subject continued study treatment.	Developed withdrawal criteria but not withdrawn	Yes	Yes	Yes	Yes
26	The subject has confirmed HBV virological breakthrough but continued study treatment.	Developed withdrawal criteria but not withdrawn	Yes	Yes	Yes	Yes
27	Accidental unblinding of treatment group of a subject or a blinded staff member prior to planned unblinding at <specify visit>.	Other	If classified as major protocol deviation, excluded from PP1 set.	No	If classified as major protocol deviation, excluded from PP2 set.	No
28	Study < specify the visit which >procedure not done at scheduled Visits.	Other	If classified as major protocol deviation, excluded from PP1 set.	No	If classified as major protocol deviation, excluded from PP2 set.	No
29	Efficacy evaluation not done at Week 44 visit	Other	Yes	No	No	No
30	Efficacy evaluation not done at Week 72 visit	Other	No	No	Yes	No
31	Study Visits not performed per protocol.	Other	If classified as major protocol deviation, excluded from PP1 set.	No	If classified as major protocol deviation, excluded from PP2 set.	No

ATTACHMENT 2

Adverse events of special interest list of preferred terms.

Adverse Event of Special Interest	Source	Preferred Term
ALT/AST elevation	(Modified) Liver related investigations, signs and symptoms (SMQ) narrow, (MedDRA v23.1)	Alanine aminotransferase abnormal Alanine aminotransferase increased Aspartate aminotransferase abnormal Aspartate aminotransferase increased Hepatic enzyme abnormal Hepatic enzyme increased Hepatic function abnormal Hypertransaminasaemia Liver function test abnormal Liver function test increased Transaminases abnormal Transaminases increased
Renal Complications	(Modified) Acute renal failure (SMQ) broad (MedDRA v23.1)	Acute kidney injury Anuria Nephropathy toxic Oliguria Renal failure Renal impairment Subacute kidney injury Blood creatinine abnormal Blood creatinine increased Creatinine renal clearance abnormal Creatinine renal clearance decreased Creatinine urine abnormal Creatinine urine decreased Crystal nephropathy Glomerular filtration rate abnormal Glomerular filtration rate decreased Nephritis Proteinuria Renal function test abnormal Renal tubular disorder Renal tubular dysfunction Renal tubular injury

Adverse Event of Special Interest	Source	Preferred Term
		Renal tubular necrosis
		Urine output decreased
		Nephropathy
		Nephropathy toxic
		Glomerulonephropathy
		Nephrolithiasis
Cholesterol increase	Dyslipidaemia (SMQ), (MedDRA v23.1)	Blood cholesterol abnormal
		Blood cholesterol esterase increased
		Blood cholesterol increased
		Dyslipidaemia
		High density lipoprotein abnormal
		High density lipoprotein decreased
		High density lipoprotein increased
		Hypercholesterolaemia
		Hyperlipidaemia
		Hypo HDL cholesterolaemia
		Intermediate density lipoprotein decreased
		Intermediate density lipoprotein increased
		LDL/HDL ratio decreased
		LDL/HDL ratio increased
		Lipid metabolism disorder
		Lipids abnormal
		Lipids increased
		Lipoprotein abnormal
		Lipoprotein increased
		Low density lipoprotein abnormal
		Low density lipoprotein decreased
		Low density lipoprotein increased
		Non-high-density lipoprotein cholesterol decreased
		Non-high-density lipoprotein cholesterol increased
		Primary hypercholesterolaemia
		Remnant hyperlipidaemia
		Remnant-like lipoprotein particles increased
		Total cholesterol/HDL ratio abnormal
		Total cholesterol/HDL ratio decreased
		Total cholesterol/HDL ratio increased
		Very low density lipoprotein abnormal
		Very low density lipoprotein decreased

Adverse Event of Special Interest	Source	Preferred Term
		Very low density lipoprotein increased
Hematologic abnormalities	(Modified) Haematopoietic cytopenias affecting more than one type of blood cell (SMQ), (MedDRA v23.1)	Aplastic anaemia Autoimmune aplastic anaemia Bicytopenia Bone marrow failure Cytopenia Febrile bone marrow aplasia Full blood count decreased Gelatinous transformation of the bone marrow Immune-mediated pancytopenia Pancytopenia Panmyelopathy Aspiration bone marrow abnormal Biopsy bone marrow abnormal Blood count abnormal Blood disorder Bone marrow disorder Bone marrow infiltration Bone marrow myelogram abnormal Bone marrow necrosis Bone marrow toxicity Haematotoxicity Myelodysplastic syndrome Myelodysplastic syndrome transformation Myelofibrosis Myeloid metaplasia Plasmablast count decreased Scan bone marrow abnormal
Hematologic abnormalities	(Modified) Haematopoietic erythropenia (SMQ), (MedDRA v23.1)	Aplasia pure red cell Aplastic anaemia Erythroblast count decreased Erythroid maturation arrest Erythropenia Hypoplastic anaemia Microcytic anaemia Proerythroblast count decreased

Adverse Event of Special Interest	Source	Preferred Term
		Red blood cell count decreased
		Reticulocyte count decreased
		Reticulocytopenia
		Anaemia
		Erythroblast count abnormal
		Erythropoiesis abnormal
		Haematocrit abnormal
		Haematocrit decreased
		Haemoglobin abnormal
		Haemoglobin decreased
		Leukoerythroblastic anaemia
		Normochromic anaemia
		Normochromic normocytic anaemia
		Normocytic anaemia
		Proerythroblast count abnormal
		Red blood cell count abnormal
		Reticulocyte count abnormal
		Reticulocyte percentage decreased
Hematologic abnormalities	(Modified) Haematopoietic leukopenia (SMQ), (MedDRA v23.1)	Agranulocytosis Band neutrophil count decreased Band neutrophil percentage decreased Basophil count decreased Basophilopenia B-lymphocyte count decreased Cyclic neutropenia Eosinopenia Eosinophil count decreased Febrile neutropenia Granulocyte count decreased Granulocytes maturation arrest Granulocytopenia Idiopathic neutropenia Leukopenia Lymphocyte count decreased Lymphopenia Metamyelocyte count decreased Monoblast count decreased Monocyte count decreased Monocytopenia

Adverse Event of Special Interest	Source	Preferred Term
		Myeloblast count decreased
		Myelocyte count decreased
		Neutropenia
		Neutropenic infection
		Neutropenic sepsis
		Neutrophil count decreased
		Promyelocyte count decreased
		Pure white cell aplasia
		T-lymphocyte count decreased
		White blood cell count decreased
		Basophil count abnormal
		Basophil percentage decreased
		B-lymphocyte abnormalities
		B-lymphocyte count abnormal
		Differential white blood cell count abnormal
		Eosinophil count abnormal
		Eosinophil percentage decreased
		Full blood count abnormal
		Granulocytes abnormal
		Leukopenia neonatal
		Lymphocyte count abnormal
		Lymphocyte percentage abnormal
		Lymphocyte percentage decreased
		Monocyte count abnormal
		Monocyte percentage decreased
		Mononuclear cell count decreased
		Myeloblast percentage decreased
		Myelocyte percentage decreased
		Myeloid maturation arrest
		Neutrophil count abnormal
		Neutrophil percentage decreased
		Plasma cell disorder
		Plasma cells absent
		White blood cell analysis abnormal
		White blood cell count abnormal
		White blood cell disorder
Hematologic abnormalities	(Modified) Haematopoietic thrombocytopenia (SMQ), (MedDRA v23.1)	Acquired amegakaryocytic thrombocytopenia
		Megakaryocytes decreased

Adverse Event of Special Interest	Source	Preferred Term
		Platelet count decreased
		Platelet maturation arrest
		Platelet production decreased
		Platelet toxicity
		Thrombocytopenia
		Megakaryocytes abnormal
		Platelet count abnormal
		Platelet disorder
		Plateletcrit abnormal
		Plateletcrit decreased

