2. GENERAL ANALYSIS DEFINITIONS

The SAP will use throughout the document the following definitions:

- *Study treatment* refers to: JNJ-3989, JNJ-6379, placebo and NA (ETV, TDF, or TAF)
- *Study agent* refers to: JNJ-3989, JNJ-6379, or placebo
- *Study intervention arm* refers to:
 - Arm 1: JNJ-3989 (100 mg) + JNJ-6379 (250mg qd) + NA
 - Arm 2: JNJ-3989 (200 mg) + placebo + NA
 - Arm 3: JNJ-3989 (100 mg) + placebo + NA
 - Arm 4: JNJ-3989 (40 mg) + placebo + NA

Arm 5: placebo + JNJ-6379 (250mg qd) + NA

Arm 6: placebo + placebo + NA

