5.4.15. Virologic Breakthrough

5.4.15.1. Definition

HBV virological breakthrough is defined as having a confirmed on-treatment HBV DNA increase by $>1 \log_{10}$ from nadir level (lowest level reached during treatment) in participants who did not have on-treatment HBV DNA level below the lower limit of quantification (LLOQ) or a confirmed on-treatment HBV DNA level $>200 \text{ IU/mL}$ in participants who had on-treatment HBV DNA level below the lower limit of quantification (LLOQ). Confirmed HBV DNA increase/level means that the criterion should be fulfilled at 2 or more consecutive time points or at the last observed time point.

On-treatment will be defined as the time period in which the participant receives any of the study interventions (including NA).

The number and proportion of participants who experience a virologic breakthrough will be summarized descriptively by intervention arm and analysis phase.

The number and proportion of participants who experience a virologic breakthrough followed by on-treatment biochemical flare will be summarized descriptively by intervention arm.

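### SAP Attachment 1 puts no time limit on PP1 deviations, so Supplementary Estimand 2 can drop participants for response-related events that follow the primary endpoint (clearest in items 21-24)

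*SAP*

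**What the plan says.** SAP 2.3 defines PP1 as the ITT set without selected major deviations that could affect assessment of the Week 48 primary endpoint, and refers to the PP1 column of Attachment 1 for the list. SAP 5.2.1 decides response from the Week 44 laboratory tests, or from an ALT re-test before Week 48. Under Protocol 6.6, participants who meet the criteria stop NA at Week 48 and the others continue it.

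Items 21-24 of Attachment 1 describe a participant who meets a re-treatment condition without starting NA. Item 22 is "Subject has confirmed HBeAg seroreversion, but did not start NA treatment" and item 24 is "Subject has a confirmed post-treatment increase in HBV DNA >20,000 IU/mL over a period of at least 4 weeks, but did not start NA treatment". All four lead to PP1 exclusion if classified as major and carry the PP1 intercurrent-event flag. Items 19 ("Subject missed NA treatment for more than 5 doses within a four week period") and 20 ("Subject received expired study medication <JNJ-3989, JNJ-6379, NA or placebo>") are treated the same way. No item has a PP1 cut-off date.

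SAP 5.2.4.1.2 runs Supplementary Estimand 2 on PP1. SAP 3.1 bases the primary analysis on all data at the cut-off, including later visits of participants already in follow-up.

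**The concern.** A per-protocol set for an endpoint should not depend on what happens after that endpoint is known. Here it can, and the later events are linked to the outcome. Among treatment completers, being at risk for items 21-24 requires being off NA, and meeting the primary endpoint is what takes a participant off NA at Week 48. Excluding someone under these items for a later event tends to remove a responder. After Week 48, missed or expired NA doses (items 19 and 20) can arise only in people still taking NA, who are largely non-responders.

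The PP1 response rates, and the differences between arms, could then move for reasons unrelated to adherence during the 48 weeks of treatment. The planned table of PP1 exclusions by arm and deviation type would not show whether an exclusion came before or after the endpoint.

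**Working it through.** **1. Timing.** The endpoint is fixed at Week 44, or at the ALT re-test before Week 48. A responder stops NA at Week 48. Items 23 and 24 need a rise lasting at least 4 weeks, so for that participant the earliest date is 48 + 4 = about Week 52. The event cannot change the Week 44 result, but under SAP 3.1 it can be in the database at the primary cut.

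**2. Columns side by side.** The PP1 and PP2 entries match for items 1-28 and 31. Only item 29 (no Week 44 efficacy evaluation) and item 30 (no Week 72 evaluation) differ. The list therefore separates the two endpoints for missed evaluations but not for conduct after Week 48.

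**3. Planning rates.** Protocol Table 7 gives min-test power 0.871 for 50% in Arm 1 against 25% in Arms 3 and 5. A simulation with the pooled normal-approximation test gives 0.870. The pairwise formula gives 0.970 and 0.889, as stated. These figures are not disputed; the check confirms that the rates are read correctly.

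**4. Possible shift.** Let p be the true rate, f the share of responders removed and g the share of non-responders removed. The removal shares are assumptions, set equal in both arms.

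PP1 rate = p(1-f) / [p(1-f) + (1-p)(1-g)]

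With f = 10%, g = 0: active 0.225/0.975 = 23.1%; control 0.045/0.995 = 4.5%. With f = 0, g = 10%: active 0.25/0.925 = 27.0%; control 0.05/0.905 = 5.5%.

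| f | g | 25% vs 5% (true difference 20.0 points) |
|---|---|---|
| 5% | 0 | 19.3 |
| 10% | 0 | 18.6 |
| 20% | 0 | 17.0 |
| 0 | 5% | 20.7 |
| 0 | 10% | 21.5 |
| 0 | 20% | 23.2 |
| 10% | 5% | 19.3 |
| 5% | 10% | 20.8 |
| 10% | 10% | 20.0 |

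For Arm 1 against Arm 3 at 50% vs 25% (25.0 points), f = 10% gives 47.4 - 23.1 = 24.3, and g = 10% gives 52.6 - 27.0 = 25.6.

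**5. Numbers of people at 10%.** Responders: 0.25 × 90 × 0.1 = 2.3 in an active arm of 90 and 0.05 × 45 × 0.1 = 0.2 in control. Non-responders: 0.75 × 90 × 0.1 = 6.8 and 0.95 × 45 × 0.1 = 4.3.

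**The case against.** The strongest reply is that SAP 2.3 already limits PP1 by purpose: a deviation after Week 44 cannot affect the Week 48 endpoint, and items 19-24 also need classification as major. A careful reviewer could screen late events out on that basis. However, Section 2.3 defers to a column that lists these items, and neither phrase sets a date.

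Identical columns do not by themselves prove an error. Early discontinuers may stop NA before Week 48 (Protocol 6.6 and 7.1), so items 21-24 can validly arise inside the PP1 window. That stands, and it is why the items should be time-limited rather than deleted from PP1.

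The SAP also concedes inherent bias in this analysis (5.2.4.1.2), and 4.5 plans a listing of major deviations. That is fair disclosure, but it does not limit event dates.

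Three stronger readings are tempting but not supported:

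- **Item 26** ("The subject has confirmed HBV virological breakthrough but continued study treatment"). Because the SAP counts NA as study treatment, a reader might infer that this item removes non-responders who stay on NA after breakthrough in follow-up. The item is coded as a withdrawal criterion not acted on. The criterion in Protocol 7.1 concerns investigational intervention only and allows NA to continue, so continuing NA alone breaches nothing.
- **Items 9-14, 28 and 31** (the last being "Study Visits not performed per protocol"). They share the missing time limit, but no clear dependence on response is shown. Scheduled follow-up visits do differ: 14 after NA stop, 12 with NA continued in Arms 1-5, and 4 with NA continued in Arm 6. At an assumed 1% per visit over full follow-up, exclusions would be 11.8% of an active arm and 4.4% of control, yet the difference would be 20.1 points.
- **The main analysis.** The PP1 intercurrent-event flag might seem to carry the problem into the mITT analysis. It acts only when endpoint data are missing; observed Week 44 values are used regardless (SAP 5.2.2 and 5.2.2.1.4).

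**Conclusion.** Wrong as written, but minor. The PP1 definition allows exclusion for events after the endpoint that are related to response. Items 21-24 tend to remove responders, and items 19 and 20 after Week 48 tend to remove non-responders. A reader might infer a known bias against the active arms; the documents do not support one, because the two groups of items pull in opposite directions and no deviation rates are given.

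The effect is likely small. An exclusion under items 21-24 needs a re-treatment condition met, NA not re-started, classification as major, and occurrence before the cut used for PP1. If PP1 membership is frozen at the primary lock, only participants already in follow-up then are exposed. The shifts calculated above rest on assumed removal shares and show scale only. The consequence is confined to Supplementary Estimand 2 of the primary endpoint.

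**What to change.** In Attachment 1, state that a post-randomisation deviation counts for PP1 only if its onset is on or before the Week 48 visit, the end of the double-blind intervention phase. This matches Supplementary Estimand 2, which counts treatment discontinuation before Week 48 as non-response. Count later events, including items 21-24 after Week 48, for PP2 only. Apply the rule to all post-randomisation items together: limiting only items 21-24 would leave items 19 and 20 removing mainly non-responders.

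The cost is one sentence in Attachment 1 and one condition in the PP1 flag derivation. SAP 4.5 has the deviation criteria finalised before the primary lock, and SAP Amendment 2 refers to past interim analyses, which by SAP 3.1 follow the primary analysis, so PP1 may already have been analysed. In that case keep the result and report the corrected set alongside it, labelled as a later correction; the cost is then one extra supplementary run.

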Data from 4 completed Phase 1 studies (56136379HPB1001, 56136379HPB1002, 56136379HPB1003 and 56136379HPB1004) in healthy and CHB participants (N 98 and 41, respectively), indicate that orally administered JNJ-6379 as single doses up to 600 mg or as multiple doses (250 mg twice daily for 2 days followed by 170 mg qd for 18 days or 150 mg twice daily for 2 days followed by 100 mg qd for 10 days) in healthy participants and as multiple doses up to 250 mg for 28 days in CHB participants was safe and well tolerated. No SAEs considered at least possibly related to the study intervention were reported. Most AEs were mild and not considered treatment-related, with no dose-related trends. Those observations were supported by the final safety data obtained for Phase 1 Study 56136379HPB1005, in which 14 healthy adult participants received single doses (300 mg) of JNJ-6379.

Safety data are also available from IAs 2 and 3 conducted for the Phase 2a Jade study, which were mentioned above. There were no deaths, SAEs considered at least possibly related to the study intervention, or AEs leading to discontinuation. Most AEs were grade 1 or 2 in severity. The majority of reported AEs were considered unrelated to JNJ-6379 by the investigator. Grade 2 to 4 AEs considered at least possibly related to JNJ-6379 by the investigator were grade 2 asthenia (3 participants), grade 4 ALT increased, grade 2 headache, grade 2 vertigo, grade 3 anemia (corrected to grade 2 by the investigator after the IA cut-off date), grade 2 hypertension, and grade 2 fatigue (all observed in 1 participant each).

Increased cholesterol is considered a laboratory abnormality of interest for JNJ-6379, based on safety review from nonclinical and clinical trials. Cholesterol increased was reported as an AE in 4 (4.1%) participants on JNJ-6379 for the pooled Phase 1 studies, in 1 (2.4%) participant on JNJ-6379 for the Phase 1 study 56136379HPB1005, and in none of the participants in the Phase 2a Jade study.

2.2.2. Combination of JNJ-3989 and JNJ-6379 with Entecavir or Tenofovir Prodrugs (Tenofovir Disoproxil Fumarate or Tenofovir Alafenamide)

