8.2.4. Clinical Safety Laboratory Assessments

Blood samples for serum chemistry, hematology, and coagulation, and a urine sample for urinalysis, urine chemistry, and renal biomarkers will be collected as noted in Section 10.2, Appendix 2, Clinical Laboratory Tests. The investigator must review the laboratory results, document this review, and record any clinically relevant changes occurring during the study in the AE section of the CRF. The laboratory reports must be filed with the source documents.

Participants need to have fasted for at least 10 hours before biochemistry samples are taken for measurement of phosphate, calcium, creatinine, and lipids. Participants are to bring their oral study intervention with them to each study visit and have that day's intake at the site.

If a grade 3 or grade 4 laboratory abnormality occurs, that is considered to be clinically significant by the investigator, a confirmatory test must be performed preferably within 48 hours but no later than 72 hours after the results have become available.

For this study, the laboratory abnormality of cholesterol increase is identified as laboratory abnormality of interest.

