6.1.3. Adverse Events of Special Interest

Incidence of treatment-emergent adverse events of special interest will be summarized by intervention arm and analysis phase.

The adverse events of special interest include:

- ALT/AST elevations
- Injection Site Reactions
- Renal complications
- Cholesterol increase
- Hematologic abnormalities (platelet count, hemoglobin, reticulocytes, neutrophil count)

The list of all preferred terms belonging to ALT/AST elevations, renal complications, cholesterol increase, and hematologic abnormalities is provided in [ATTACHMENT 2](#). Injection site reactions will be identified using the eCRF Injection Site Reaction form.

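### The 'Cholesterol increase' event of special interest also counts preferred terms for decreases in lipoprotein fractions and ratios

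*SAP*

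**What the plan says.** SAP Section 6.1.3 lists "Cholesterol increase" among five adverse events of special interest. It then says "The list of all preferred terms belonging to ALT/AST elevations, renal complications, cholesterol increase, and hematologic abnormalities is provided in" Attachment 2, and adds: "Incidence of treatment-emergent adverse events of special interest will be summarized by intervention arm and analysis phase". Membership of the category is thus having any listed term, and no rule on direction is given.

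Attachment 2 fills the category from the MedDRA Dyslipidaemia query. The list includes "Low density lipoprotein decreased", "LDL/HDL ratio decreased" and "Non-high-density lipoprotein cholesterol decreased". It is the only row of Attachment 2 whose source is not labelled as modified.

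The protocol describes the concern in one direction only. Section 2.2.1 says: "Increased cholesterol is considered a laboratory abnormality of interest for JNJ-6379, based on safety review from nonclinical and clinical trials". Section 8.2.4 says that "the laboratory abnormality of cholesterol increase is identified as laboratory abnormality of interest". Section 2.3.3 likewise speaks of events related to a cholesterol increase.

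**The concern.** The row label and its contents do not match. Anyone reading the table will take the row as the share of participants with a rise in cholesterol, while the plan as written also counts some falls. Increased cholesterol was identified in advance as a finding of interest for JNJ-6379, so the two JNJ-6379 arms will be read against control on this row. Mixing opposite events makes that comparison harder to interpret, and small counts can shift visibly.

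Such events can enter the data. Protocol Appendix 4 includes laboratory abnormalities in the adverse event definition, and Section 8.2.4 requires clinically relevant laboratory changes to be recorded as adverse events. LDL and HDL cholesterol are in the central laboratory panel (Appendix 2), and lipid-lowering drugs are permitted with caution (Section 6.5, Table 5).

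**Working it through.** The plan gives no figure to reproduce. The check is a count of the terms, a comparison with the other lists, and the effect of one participant.

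**Step 1: count by wording** (SAP Attachment 2, 'Cholesterol increase').

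| Wording | Terms |
|---|---|
| increased | 12 |
| abnormal (no direction) | 7 |
| decreased | 7 |
| low-HDL diagnosis (Hypo HDL cholesterolaemia) | 1 |
| other diagnoses (such as dyslipidaemia, hypercholesterolaemia) | 6 |
| Total | 12 + 7 + 7 + 1 + 6 = 33 |

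Low or decreased terms: 7 + 1 = 8, and 8/33 = 24%.

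**Step 2: sort the eight.**
- Plainly the opposite event (4): LDL, VLDL, IDL and non-HDL cholesterol decreased.
- Not a cholesterol increase, but less clearly opposite (4): LDL/HDL ratio decreased, total cholesterol/HDL ratio decreased, HDL decreased, Hypo HDL cholesterolaemia. A ratio can fall because HDL rises, and low HDL is itself a dyslipidaemia finding.

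**Step 3: compare with the other lists in Attachment 2.** The ALT/AST list has no decreased term. The renal list mixes wording, but every directional term points to impairment (creatinine up, clearance or filtration down). The hematologic lists have decreased terms and no increased ones. Only the cholesterol list pairs opposites: all seven decreased terms have an increased counterpart.

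**Step 4: effect of one participant.** Incidence is participants with at least one listed term divided by arm size. With the planned sizes (protocol Section 4.1):
- arm of 90: 1/90 = 1.1 points
- arm of 45: 1/45 = 2.2 points

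SAP Section 1.4 mentions about 5% extra enrollment. If spread evenly, the sizes are 90 × 1.05 = 94.5 and 45 × 1.05 = 47.25, and the effects are 1/94.5 = 1.1 and 1/47.25 = 2.1 points.

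**Step 5: what remains after the fix.** Removing four terms and moving four leaves 33 − 8 = 25 under 'Cholesterol increase'.

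**The case against.** The signal is mainly a laboratory one, and that analysis keeps direction. SAP Section 6.2.1 derives the worst grade separately for low and high values, Section 6.2.2 uses low/normal/high shift tables, and the DAIDS table in protocol Appendix 9 grades cholesterol and LDL only as high. SAP Section 6 makes all safety summaries descriptive, and Section 6.1.2 tabulates all treatment-emergent events and lists those of special interest, so the underlying terms stay visible. All of this stands. It limits the consequence but does not correct the count in the special-interest row.

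It can also be argued that low HDL and altered ratios were kept on purpose, to capture dyslipidaemia broadly. The documents do not rule this out for those four terms. It cannot explain decreases in LDL, VLDL, IDL or non-HDL cholesterol.

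Of those four, only LDL is in the central panel of protocol Appendix 2, so the LDL term is the likeliest route in practice. That narrows the exposure without removing it.

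A reader might set the per-participant effect against the Phase 1 adverse event rates of 4.1% and 2.4% in protocol Section 2.2.1. That comparison is unsafe. The same sentence reports none in the Phase 2a study. The 2.4% is given for one participant in a study that dosed 14, where 1/14 = 7.1%. Nothing says those rates were counted with this 33-term list.

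**Conclusion.** The mismatch is real and minor. Following the SAP as written puts some lipid decreases into a row named for an increase. The mismatch is firm for four terms and softer for four more. The size is 1.1 points per affected participant in an arm of 90 and 2.2 points in an arm of 45. This assumes that the participant has no other listed term in that phase and that arms are near their planned size. How many participants would be affected is unknown.

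Three stronger readings are tempting and not supported:
- A reader might infer that any fall in cholesterol is counted. No term for a decrease in total blood cholesterol is listed, so only falls in the listed fractions or ratios enter.
- A reader might infer a bias against JNJ-6379. The same list applies to every arm. The error is misclassification, and nothing in the documents fixes the direction of its effect on a comparison between arms.
- A reader might infer that the whole MedDRA query was taken over unedited. The missing label is suggestive, but the content of the query is not in the documents.

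**What to change.** In SAP Attachment 2, remove the decreased terms for LDL, VLDL, IDL and non-HDL cholesterol from 'Cholesterol increase'. Report the two decreased-ratio terms and the two low-HDL terms on a separate line for other lipid abnormalities. Label the source as modified, as in the other rows.

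The 25 remaining terms still include seven that say only abnormal and a few that are not specific to cholesterol level, such as lipid metabolism disorder and cholesterol esterase increased. The ALT/AST list also keeps abnormal terms, so these can stay, but the row should then be read as a sensitive capture and not as a strict count of increases.

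No new data are needed and no efficacy analysis changes. The cost is regenerating special-interest tables already produced: Attachment 2 dates from SAP Amendment 1, and Amendment 2 refers to interim analyses already done. The change should be recorded as made after those analyses.
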